7.3.2.1. Additional Pregnancy Detection Measures

- All female subjects of child bearing potential will be invited to the site for an unscheduled visit as soon as the site's Principal Investigator receives and signs Amendment #5.
- The subject should be informed of the new safety issue regarding pregnancy. The issue of contraception should be reminded and emphasized.
- The Appendix to the Informed Consent should be signed.
- All female subjects of child bearing potential will be provided with home urine pregnancy test kits.

7.3.3. Termination Visit

Termination Visit (6) / (Week 36 ± 3 days) of LAQ/5063 Active Double-Blind Phase (Completion of the full 36 weeks or as requested by the sponsor), or any Termination or Early Discontinuation visit occurring as long as the Sponsor continues the development of laquinimod 0.6 mg for RRMS.

In the event of early discontinuation, standard termination procedures will be followed.

Early discontinuation is defined as withdrawal from the study prior to the completion of the full study period:

- Withdrawal prior to completion of 24 months of the first period of open label phase.
- Subjects that chose to continue to the second period of open label phase (additional 36 months), and did not complete this period.
- Subjects that chose to continue treatment from Month 60 as long as the Sponsor continues the development of laquinimod 0.6 mg for RRMS and did not complete this period.

Subjects who are discontinued from study treatment will be encouraged to continue all scheduled visits and procedures until completion of the study (with the exception of procedures associated with drug dispensing and accountability, pregnancy testing, and GFR estimation [including body weight measurement]).

Subjects who have completed 24 months of open label phase and chose not to continue to further extension of open label phase will be regarded as completers.

Subjects who have completed 60 months of the extension open label phase and chose not to continue to further extension of open label phase (as long as the Sponsor continues the development of laquinimod 0.6 mg for RRMS) will be regarded as completers.

The reason for discontinuation of therapy will be documented in the source documents and captured on the CRF. If there are several reasons for early discontinuation, the more severe will be chosen as the primary reason. In the event that laquinimod is discontinued early, an early termination visit should be completed as close to the last dosing date as possible.

Subjects who did not complete the 36 weeks of treatment of LAQ/5063 active double-blind phase until approval of amendment No 2 will be called for an a termination visit of the active double-blind phase as requested by the Sponsor to be switched to the open-label phase (LAQ/5063 OL)

In case a subject completed the 60 months OL period, but decided not to proceed with the further extension, he/she will be considered as completer.

The following will be performed at the Termination visit of LAQ/5063 active double-blind phase (completion of the full 36 weeks or as requested by the Sponsor), and/or at any early discontinuation visit occurring as long as the Sponsor continues the development of laquinimod 0.6 mg for RRMS:

- Vital signs, including weight
- Complete physical examination
- Record of AEs: If an AE is still ongoing, or a new AE is present at the termination visit, it will be followed according to the discretion of the Investigator and recorded in the subject's source documents and in the CRF (see Section 7.3.4).
- IMP accountability
- Subject compliance
- Review concomitant medication. Note: moderate/strong CYP3A4 inhibitors are disallowed during the 30 days after the last dose has been administered. For information on the use of CYP1A2 substrates following laquinimod cessation, please refer to the laquinimod IB.

- ECG
- Complete neurological examination, including FS, AI, and EDSS, and 25 foot walk test
- MSFC (this is relevant for LAQ/5063 active double-blind phase only)
- Evaluation of relapses (if applicable). If a relapse is confirmed or ongoing at the termination visit, it will be followed until relapse stabilization. All follow-up evaluations must be documented in the source documents and the CRF.
- Laboratory tests
 - Hematology
 - Serum chemistry (including GFR estimation)
 - Serum pregnancy test (β -hCG) for women of child-bearing potential
 - Blood sampling for PK study (ancillary study in sub-group of subjects. For subjects participating in this study, the IMP will be administered at the site. This is relevant for LAQ/5063 active double-blind phase only)
 - Blood sampling for PPK study (ancillary study in all subjects). (This is relevant for LAQ/5063 active double-blind phase only)
 - For a detailed sampling plan for PK and PPK studies refer to Section 8.4. (This is relevant for LAQ/5063 active double-blind phase only)
- For all subjects who are female of child-bearing potential:
 - The use of effective contraception will be ascertained (should be recorded in the source documents) and all subjects will be reminded to continue using two acceptable methods of contraception up to 30 days from the date of the last dose of the IMP
 - Subjects will be instructed about the potential teratogenicity and delayed risks for a child exposed in uterus to laquinimod
 - Female subjects of child-bearing potential will be reminded about (should be recorded in the source documents) importance of stopping the study drug and informing the site in any case of suspected pregnancy (positive home urine test result, delay of menstruation or any other reason suggesting pregnancy)
- Call IVRS for update on subject's termination (This is relevant for LAQ/5063 active double-blind phase only)

Notification of the Sponsor in the event of early discontinuation including the reason for termination (see Section 7.3.4)

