4. STUDY OBJECTIVES

- To make treatment with laquinimod available to all subjects who previously participated in LAQ/5062 study and those who completed the Termination visit of LAQ/5063 active double-blind phase (completion of the full 36 weeks or as requested by the Sponsor).
- To assess the long-term safety, and tolerability in the group that received active treatment in LAQ/5062 protocol and additional short term safety and tolerability in the group who received placebo treatment. LAQ/5063 OL phase will assess long-term safety and tolerability of 0.6 mg laquinimod once daily.

Further efficacy data will be obtained by comparing baseline to termination in the group who received placebo treatment in LAQ/5062 core study protocol.

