4.1.2. Tolerability

- Number and percentage of subjects who prematurely discontinued from the study
- Number and percentage of subjects who prematurely discontinued from the study due to AEs

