Physical Examination	X	X	X	X	X	X	X	X	X	X
Safety Laboratory Tests (including inflammatory markers, GFR estimation)	X	X	X	X	X	X	X ^h	X ^h	X ^h	X ^h
Laquinimod Dispensing, & Accountability	X	X	X	X	X	X	X ⁱ	X	X ⁱ	X
Subject Compliance	X	X	X	X	X	X	X	X	X	X
Termination Documentation & Notification of Early Termination								X		

Procedure/Visit Number	V10	V11	V12	V13	V14	V15	V16	Every 6 months	Termination	Unscheduled Visit
Months	24	30	36	42	48	54	60		Early Discontinuation	Unscheduled visit ^a
Unscheduled samples										X ^j

Subjects who are discontinued from study treatment will be encouraged to continue all scheduled visits and procedures until completion of the study (with the exception of procedures associated with drug dispensing and accountability, pregnancy testing, and GFR estimation [including body weight measurement]).

^a Assessments during an unscheduled visit will be performed as deemed necessary by the Investigator, except for vital signs and adverse events, which are mandatory at each visit

^b At Month 24 (visit 10) of the open label phase Informed Consent will be signed for the extended open label period of 36 months. At Month 60 (visit 16) of the open label phase an Informed Consent will be signed for the additional extension as long as the Sponsor continues the development of laquinimod 0.6 mg for RRMS

^c In addition, an evaluation should take place as soon as possible for subjects already in the study, following approval of Amendment #10

^d Relapse evaluation will be performed in scheduled as well as unscheduled visits as deemed necessary by the Investigator/Coordinator

^e For women of child-bearing potential

^f Mandatory phone calls will be performed within 72 hours of the scheduled home pregnancy test

^g Weight will be measured at all visits

^h Inflammatory markers will not be collected from Month 60 and onwards

ⁱ Only drug retrieval

^j Unscheduled urgent safety laboratory samples, pharmacokinetic blood samples, and/or samples for potential biomarker analyses may be collected at the discretion of the investigator or medical monitor at any time to assist with further investigations of cardiovascular events or other clinical event of interest. The samples should be collected as soon as possible in association with the event.

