11.5.5. Drug Tolerability & Drop-Out Assessment

The number and percentage of subjects who failed to complete the study will be presented by treatment groups.

The number and percentage of subjects who prematurely discontinued from the study due to AEs will be presented by treatment groups.

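### Subjects who decline extension at Month 24 or 60 enter neither tolerability count, while the same exit at a later visit counts as early discontinuation

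*Combined protocol and SAP*

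**What the plan says.** The objective is in Section 4: "LAQ/5063 OL phase will assess long-term safety and tolerability of 0.6 mg laquinimod once daily". Section 4.1.2 lists two tolerability outcomes, both counts of premature discontinuation from the study: one for any cause, the other "Number and percentage of subjects who prematurely discontinued from the study due to AEs". Section 11.5.5 carries these into the analysis. Its first line is "The number and percentage of subjects who failed to complete the study will be presented by treatment groups"; its second gives the count due to adverse events.

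Section 7.3.3 decides who is a completer.

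- Month 24: subjects who "completed 24 months of open label phase and chose not to continue to further extension of open label phase will be regarded as completers".
- Month 60: "In case a subject completed the 60 months OL period, but decided not to proceed with the further extension, he/she will be considered as completer".
- Early discontinuation between Months 24 and 60: "Subjects that chose to continue to the second period of open label phase (additional 36 months), and did not complete this period".
- Early discontinuation after Month 60: "Subjects that chose to continue treatment from Month 60 as long as the Sponsor continues the development of laquinimod 0.6 mg for RRMS" and then leave before that period is complete.

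The boundaries follow the consent calendar. A footnote to Table 7 (Section 7.2) states: "At Month 24 (visit 10) of the open label phase Informed Consent will be signed for the extended open label period of 36 months". The same footnote places the next consent at Month 60, for an extension that lasts as long as the sponsor pursues the 0.6 mg dose.

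**The concern.** Whether a stop is counted depends on when it happens, not on why. A subject who gives up laquinimod at Month 24 because of an adverse event or lack of effect, and does so by not signing the next consent, is a completer and enters neither count. A subject who signs and stops at the next six-monthly visit for the same reason is an early discontinuation.

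After Month 60 the difficulty is different. The period ends only when the sponsor stops development, so every exit before then is premature by definition. The percentage therefore rises with study length even if the rate of stopping never changes.

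At stake is whether the one tolerability measure in the plan answers the long-term objective. A decision not to continue an oral treatment after two or five years can be a tolerability decision, and the plan has no planned table in which it would be reported.

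**Working it through.** The plan states no discontinuation rate, sample size or dropout assumption for this point, so there is no figure to reproduce. The check has four steps.

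**1. The same exit under the written rules**

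| Exit | Class in 7.3.3 | Counted under 4.1.2 and 11.5.5? |
|---|---|---|
| Declines at Month 24 | Completer | No |
| Continues, leaves at Month 30 | Early discontinuation | Yes |
| Declines at Month 60 | Completer | No |
| Continues, leaves at Month 66 | Early discontinuation | Yes |

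All-cause stopping is the sum of the counted and uncounted rows, so the reported figure cannot exceed it. The direction is fixed.

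**2. What the documents' own counts can show**

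Inputs: up to 264 subjects expected to enter LAQ/5063 (Section 11), and 110 ongoing at Amendment 10 (Section 21.1).

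Exits: 264 − 110 = 154, and 154/264 = 58.3%.

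Let s be the share of these exits that fell at Month 24 or 60. The documents do not give s; the values below are assumptions. Reported percentage = 154 × (1 − s)/264.

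| s | Reported as premature |
|---|---|
| 0% | 58.3% |
| 25% | 43.8% |
| 50% | 29.2% |
| 75% | 14.6% |
| 100% | 0% |

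This is a bound, not an estimate. The 264 is an expected maximum at double-blind entry; open-label entry is not given, and some of the 154 may have left before the open-label phase began.

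**3. Illustrative open-label cohort to Month 84**

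Assumptions: a constant exit probability h per six months, plus a probability e of declining at each of Months 24 and 60. Month 24 follows 4 intervals, Month 60 follows 10, Month 84 follows 14. With q = 1 − h:

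- Reported = (1 − q⁴) + q⁴(1 − e)(1 − q⁶) + q¹⁰(1 − e)²(1 − q⁴)
- Declined = q⁴e + q¹⁰(1 − e)e

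For h = 2% and e = 10%: reported = 0.0776 + 0.0948 + 0.0514 = 22.4%; declined = 0.0922 + 0.0735 = 16.6%; all-cause = 39.0%.

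| h | e | Reported | Declined | All-cause |
|---|---|---|---|---|
| 1% | 5% | 12.5% | 9.1% | 21.6% |
| 2% | 10% | 22.4% | 16.6% | 39.0% |
| 3% | 20% | 28.7% | 29.5% | 58.2% |

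**4. Dependence on duration after Month 60**

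Take subjects who continue at Month 60, with a constant 2% exit per six months (assumed). If the study ends at Month 84, 1 − 0.98⁴ = 7.8% are premature. If it ends at Month 120, 1 − 0.98¹⁰ = 18.3% are. The rate of stopping is identical in both cases; only the duration differs.

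**The case against.** The strongest reply has five parts.

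- **Subjects can leave at any time.** Section 7.3.4 sets no time limit on withdrawal and lists adverse event and lack of efficacy among the reasons. Declining the Amendment 10 re-consent (Section 7.3.2) carries no completer status. This stands. A reader might infer that Months 24 and 60 are the points at which dissatisfied subjects can leave; the text supports only that they are the points at which leaving is not counted.
- **Nothing is concealed.** The rule is openly pre-specified and follows the consented periods. The reason for stopping therapy goes on the CRF (Section 7.3.3), action taken is recorded for each adverse event (Section 10), and adverse events are tabulated by it (Section 11.5.1). A reader might infer that the plan hides tolerability-driven exits or treats them as successes; the documents do not support this. However, the adverse event tables do not give all-cause stopping, nothing expressly requires a reason from a completer, and the Section 7.3.4 list has no entry for declining an extension.
- **Section 11 is written around 36 double-blind weeks.** It does not say that Section 11.5.5 uses the Month 24 and 60 definitions. That is fair, but Section 7.3.3 is the only definition of completion in the document, and Section 18.4.2 ties the analysis to what the protocol defines. Appendix 4 mentions an analytical plan, but only for scoring the MSFC.
- **The post-Month-60 percentage still carries information.** This stands in part: it mixes tolerability with duration and does not measure duration alone. The AE-specific count remains easier to interpret.
- **The study is exploratory and uncontrolled in its open-label phase, and the numbers prove no size.** Both are true. They limit the weight of the point, not its direction.

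**Conclusion.** The point holds as a defect in the outcome definition. Followed as written, the plan leaves every Month 24 and Month 60 decliner out of both tolerability counts, and pools unequal, open-ended follow-up into a crude percentage. This rests on reading the terms in Sections 4.1.2 and 11.5.5 through Section 7.3.3.

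Reported premature discontinuation will equal all-cause stopping only if nobody stops by declining; otherwise it will be lower. The size cannot be determined. The gap of 16.6 percentage points in the middle scenario rests wholly on assumed rates, and the 0% to 58.3% bound excludes nothing. A reader might take the 154 exits as evidence that many subjects left at the consent points for tolerability reasons; the documents give neither the timing nor the reasons.

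In a descriptive extension with no hypothesis test, this is a change that should be made, not one that invalidates the study.

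**What to change.** Keep completer in Section 7.3.3 as a disposition label. In Section 11.5.5:

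- **Decliners.** Report subjects who decline at Months 24 and 60 as a separate category, with reasons where recorded. Capture the reason prospectively at those visits with the Section 7.3.4 list. The same consent points recur for returning subjects (Table 12), so later collection still has value.
- **Time to event.** Add Kaplan-Meier time to permanent laquinimod discontinuation from the first open-label 0.6 mg dose.
  - All-cause curve: decliners count as stops; censor at the sponsor's end of study or the data cut.
  - AE-related curve: a decliner is an event only when the recorded reason is an adverse event; other stops are treated as censored or as competing events, stated in advance.

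The second item is feasible for past exits, because source records should hold the dates on which study drug was started and finished (Section 15.2). It also picks up subjects who stop the drug but remain in follow-up (Section 7.1), whom a count of leaving the study can miss. All voluntary stops enter the all-cause curve, including planned pregnancy, so it should be read beside the AE-related curve.

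Cost: wording in Section 11.5.5 and an existing reason list applied at two visits. The stopping figure will look less favourable, and reasons may be missing for subjects already past those visits.

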Laquinimod demonstrates a predictable and linear pharmacokinetics (PK) profile (see Section 3.3.1) characterized by high plasma protein binding (>98%), high oral bioavailability (~90%), low oral clearance (~0.09 L/h), low apparent volume of distribution (~10 L) and long half-life (~80 h). Laquinimod is extensively metabolized predominantly by cytochrome P450 (CYP) 3A4.

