3.3.1. Clinical Pharmacology Studies

Laquinimod is considered to have high oral bioavailability with linear, time independent and predictable PK, characterized by high plasma protein binding (>98%), high oral bioavailability (~90%), low oral clearance (~0.09 L/h), low apparent volume of distribution (~10 L), and long half-life (~80 h). Absorption under fasting conditions is rapid and maximal plasma levels attained generally within 1 hour after laquinimod administration. Concomitant administration with a high-fat high-calorie meal results in reduction of the absorption rate reflected by prolongation of the time to maximal plasma drug concentration (T_{max}) to approximately 5 hours and reduction of the maximum plasma concentration (C_{max}) by 30%. Food however did not significantly affect the overall extent of absorption area under the concentration by time curve (AUC).

Laquinimod is extensively metabolized, predominantly by CYP3A4. Laquinimod metabolites levels in plasma are very low and parent laquinimod is the main systemically circulating entity. Laquinimod PK is affected by moderate and strong CYP3A4 inhibitors (2.5- and 3.1-fold

increase in laquinimod systemic exposure, respectively) and strong CYP3A4 inducers. At doses of 0.6 and 1.2 mg, laquinimod is a weak inhibitor of CYP3A4 and a strong inducer of CYP1A2. For additional information, please refer to the IB.

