7.3.4.1.2. Pregnancy

To further emphasize the importance of use of effective contraception and avoidance of pregnancy under laquinimod exposure, and to reduce as much as possible the exposure to laquinimod if a pregnancy occurs despite all recommended measures, all subjects who are women of childbearing potential will be instructed about the potential teratogenicity and delayed risks for a child exposed in uterus to laquinimod.

To strengthen the preventative measures, the measures for pregnancy prevention now include: a requirement for two contraception methods (as recommended by the DMC) and a requirement for using a contraception method 30 days prior to enrollment. Furthermore, a serum β -hCG test prior to enrollment and additional follow up measures and clarifications are added. These subjects will also be counseled about the importance stopping treatment immediately if

pregnancy is suspected (positive urine β -hCG test result, delay of menstruation or any other reason suggesting pregnancy).

Acceptable methods of birth control include intrauterine devices, barrier methods (condom or diaphragm with spermicide), and hormonal methods of birth control (oral contraceptive, contraceptive patch, long-acting injectable contraceptive).

The subjects' understanding of the importance of preventive pregnancy measures and their ability to follow the required instructions will be ensured by the investigator and documented in source documents.

Additionally, monthly pregnancy tests (urine dipstick and/or serum pregnancy β -hCG test, as applicable per the relevant time point) will be performed (except for where subjects have discontinued study drug but are continuing to attend study visits for follow-up).

All pregnancies of women participating in study and that occur during the study, or within 30 days after the last dose of treatment was administered, are to be reported immediately to the individual identified in the clinical study personnel contact information section of this protocol, and the investigator must provide the LSO/CRO with the pregnancy form. The process for reporting a pregnancy is the same as that for reporting a SAE (see Section 10).

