Important medical events are those which may not be immediately life-threatening, but may jeopardize the subject and may require intervention to prevent one of the other serious outcomes listed above. Examples of such events are intensive treatment in an emergency room or at home for allergic bronchospasm; blood dyscrasias or convulsions that do not result in hospitalization; resulting in an AE will normally be considered serious by this criterion.

Inpatient **hospitalization** or prolongation of existing hospitalization means that hospital inpatient admission and/or prolongation of hospital stay were required for treatment of AE, or that they occurred as a consequence of the event. It does not refer to pre-planned elective hospital admission for treatment of a pre-existing condition that has not significantly worsened, or to diagnostic procedure. It does not refer either to hospitalization for iv steroid treatment of a relapse, unless it is a worsening of condition beyond expected disease progression.

The term "**life-threatening**" in the definition of "serious" refers to an event in which the subject was at risk of death at the time of the event; it does not refer to an event which hypothetically might have caused death if it were more severe.

Any new SAE that occurs after the study period should be recorded and reported immediately (cross reference to the Pharmacovigilance section). The study period for the purpose of SAE reporting is defined as the period from the subject's signature on the informed consent form until the end of the follow-up period (30 days following last dose).

SAE Reporting

In order to satisfy regulatory requirements, any SAE, whether deemed IMP-related or not, must be reported to the contract research organization (CRO) as soon as possible after the investigator or coordinator has become aware of its occurrence. The SAE form completion and reporting must not be delayed even if all of the information is not available at the time of the initial contact.

The SAE should be submitted within 24 hours of becoming aware of the event to the CRO. The CRO will forward the report to the appropriate Pharmacovigilance unit at Teva or Local Safety Officer who will forward the SAE report to the Global Pharmacovigilance Unit:

SAEs originating in Europe and rest of the world should be sent to:

Global Drug Safety and Pharmacovigilance Unit (Israel)
[REDACTED]

SAE originated in USA will be sent to:

Teva USA clinical safety mailbox

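### No visit or call is scheduled in the 30-day post-dose safety window for subjects whose termination visit is their last, so new events there may be missed

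*Combined protocol and SAP*

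**What the plan says.** **The window.** Section 10 defines the period for SAE reporting as running from consent "until the end of the follow-up period (30 days following last dose"). Section 7.3.4.1.2 asks that pregnancies arising during the study or "within 30 days after the last dose of treatment was administered, are to be reported immediately". Section 7.3.3 keeps two contraceptive methods in force for the same 30 days and notes that "moderate/strong CYP3A4 inhibitors are disallowed during the 30 days after the last dose has been administered".

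**The last visit.** For early discontinuation of laquinimod, Section 7.3.3 says "an early termination visit should be completed as close to the last dosing date as possible". In Tables 7 and 12 the termination column provides only for retrieval of drug, so dosing has ended by then. None of Tables 5, 6, 7 or 12 has a column after termination.

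**Who keeps being seen.** The Synopsis and Sections 5.1, 7.1 and 7.3.2 keep subjects who stop treatment on the visit schedule. Sections 7.3.3 and 7.3.4 say, less firmly, that they "will be encouraged to continue all scheduled visits and procedures until completion of the study". Section 7.3.4 requires the early termination visit of subjects who leave and decline, or are unable, to keep to the schedule. It also tells sites to try to follow them, with no date, content or form.

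**Other provisions.** AEs present at the last visit are followed until they resolve to baseline or are stable or chronic (7.3.4). Relapses open at termination are followed (7.3.3). Liver stops have at least four weeks of at least weekly enzyme tests (Appendix 10, item 1.2.1). Under Section 10, a new SAE is reportable even after the study period.

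**The concern.** The protocol names a follow-up period and gives it a length, but schedules nothing inside it. For a subject whose termination visit is the last contact, an event that begins in the following 30 days reaches the database only if the subject or another physician tells the site, or if the site's undated effort to follow leavers happens to find it.

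This matters because long-term safety and tolerability are the main objectives (Section 4), and because Amendment #10 was written after cardiovascular findings at higher doses (Sections 3.4.1.7 and 21.1). Section 10.1 asks for ischemic cardiac and cerebrovascular events to be reported within 48 hours, which presupposes that the site hears of them. Subjects who leave because of an adverse event may be at higher risk than those who stay, so incomplete ascertainment in leavers would tend to flatter the safety profile.

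**Working it through.** **1. Check the half-life.** Section 3.1.2 gives a "long half-life (~80 h"). Section 3.3.1 gives "low oral clearance (~0.09 L/h") and "low apparent volume of distribution (~10 L"). Half-life = ln 2 × V / CL = 0.693 × 10 / 0.09 = 77 h. This agrees with the stated 80 h within the rounding of the inputs.

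**2. Drug remaining after the last dose.** Assuming first-order decline, the fraction left = 0.5^(24 × days / 80).

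| Day | Half-lives elapsed | Fraction left |
|---|---|---|
| 0 | 0 | 100% |
| 3 | 0.9 | 54% |
| 7 | 2.1 | 23% |
| 14 | 4.2 | 5% |
| 30 | 9.0 | 0.2% |

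With 77 h in place of 80 h, the values at days 3, 7 and 14 are 52%, 22% and 5%. Exposure is substantial for about two weeks after the last dose and negligible by day 30. A contact at about day 30 therefore looks back over all the relevant exposure.

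**3. Who has a scheduled contact in the 30 days.**

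| Subject | Next scheduled contact after the termination visit or last dose |
|---|---|
| Stops drug, stays on visits | Next scheduled visit; up to 6 months away after Month 24, so events are collected by recall |
| Stops under a liver rule | Enzyme tests at least weekly for at least 4 weeks |
| Leaves and will not or cannot continue visits | None |
| Completes Month 24 or Month 60 and does not go on | None |
| On drug when the study ends | None; continued visits run only to study completion |

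**4. Length of the gap.** If the last visit falls 0, 3 or 7 days after the last dose (assumed delays; the documents give none), 30, 27 or 23 days of the window remain: 100%, 90% or 77%.

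**5. Person-time at study end.** Section 21.1 reports 110 ongoing subjects. If all are on drug and stop together:
- visit on day 0: 110 × 30 / 365.25 = 9.0 person-years;
- visit on day 3: 110 × 27 / 365.25 = 8.1 person-years;
- visit on day 7: 110 × 23 / 365.25 = 6.9 person-years.

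**6. What cannot be computed.** The documents give no event rate after stopping and no rate of spontaneous reporting, so the number of missed events is unknown. As an illustration only, assume a constant event rate and let c be the share of events after the last visit that are reported unprompted. The share of the 30-day events missed in these subjects is (1 − c) × (30 − v) / 30, for a last visit on day v from 0 to 7. With c = 0, 0.5 or 0.8 this is 77–100%, 38–50% or 15–20%. The result depends almost entirely on c, which is assumed.

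**The case against.** The strongest reply is that the protocol does not abandon people who stop drug. Four places keep them on scheduled visits, and Section 7.3.4 reserves the early termination visit for those who will not or cannot continue. Events open at the last visit are followed, SAEs are followed to resolution or stability, clinically significant laboratory changes are repeated, pregnancies within 30 days are reported and followed to outcome, and SAEs remain reportable without a time limit. Women are also reminded at termination about contraception and about telling the site of a suspected pregnancy.

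Most of this stands, and it rules out three stronger readings that a reader might infer:

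- *That nobody is contacted after the last dose.* The text contradicts this for subjects who stay on visits and for liver stops. The timing rule in Section 7.3.3 is also limited to early discontinuation; it sets no timing for completers or for study end.
- *That late harms are under-counted as a matter of fact.* Without event or reporting rates, only a risk of missing them is supported.
- *That the gap can be sized by taking 264 − 110 = 154 earlier leavers, or 154 × 30 / 365.25 = 12.6 person-years.* Section 11.1 expects fewer than 264 entrants, so 154 is a ceiling. It would include any deaths and losses to follow-up that no call could reach. Those subjects also left before Amendment #10 added the continued-visit text, and a change now cannot recover their data.

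What the reply does not meet is the position of subjects whose termination visit is their last. Following events already open does not find new ones, and a duty to report helps only once the site knows of the event. The instruction to pursue early leavers does not extend to completers or to study end.

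**Conclusion.** The point holds in a limited form. For leavers who will not or cannot continue visits, completers who stop at Month 24 or 60, and subjects on drug at study end, nothing is scheduled in the 30 days that the protocol itself sets for safety reporting. New events there may be missed while drug is still present.

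The exposed time at study end is at most about 9.0 person-years, or 6.9 if the last visit falls a week after the last dose. This assumes that all 110 ongoing subjects are on drug and stop together. It is uncontacted time, not a count of lost events. The residual-drug figures assume first-order decline with an 80-hour half-life.

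How many subjects fall into the first group is uncertain. Continued follow-up is stated as a rule in some sections and as encouragement in others. Section 7.3.3 also asks for an early termination visit whenever drug is stopped early, while Section 7.3.4 asks for it only from subjects who will not continue. These passages should be reconciled.

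The gap is modest but cheap to close, and it bears on the study's main objective.

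**What to change.** Add to Section 7.3.3, and to the termination column of Tables 7 and 12, one telephone contact at about 30 days after the last dose for every subject whose termination visit is their last: early leavers, completers who do not go on, and all subjects at study end. Record new SAEs (including the cardiac and cerebrovascular events of Section 10.1), other new AEs, and pregnancy. In Section 11.5.1, report events found at this contact as post-treatment follow-up events, separately identifiable, with the number of subjects due a call and the number reached.

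The SAE and pregnancy items follow directly from the protocol's own 30-day window. Asking about other AEs goes a little beyond it, but adds almost nothing to the call.

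The cost is one call and a short CRF page per subject; sites already make monthly calls about home pregnancy tests. Reported event counts may rise slightly. No dose, eligibility rule or endpoint changes.
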